The proposed study has two primary goals and each goal has an associated study phase. The primary goal of **Phase 1** is to augment the effects of post-retrieval propranolol observed in the R21. To achieve this goal, participants will receive 40 mg propranolol, 80 mg propranolol, (immediate release) or placebo immediately following each of two, retrieval CCE sessions in which exposure to standardized cocaine stimuli will serve to retrieve/reactivate memories for learning that subserves cocaine craving and cue reactivity (see figure 3). The two retrieval CCE session will be completed 24-hours apart and will be followed, two days later, by a third unmedicated test/follow-up CCE session. This two-day interim period will allow for the complete clearance of propranolol; Participants will be compensated \$75 to remain abstinent during this period. Multiple assessments of craving and physiological reactivity will be obtained at baseline and after stimulus presentations in all three CCE sessions (content and timing of stimulus

presentation in each session are detailed below in the Procedure section below). Participants will remain in MUSC's CTRC on the evening of each of the propranolol treated retrieval sessions of Phase 1 to prevent drug use.

The primary goal of **Phase 2** will be to assess the effects of post-retrieval propranolol on indices of cocaine use obtained over a 6-week follow-up in which abstinence is no longer reinforced. Drug use will be retrospectively evaluated during weekly interviews using a calendar-based assessment and urine drug screens will be performed 3 times each week to provide an objective assessment of drug use/abstinence. At week 1, 3 and 6, laboratory-based test/follow-up CCE sessions (similar to identical to the test CCE session in Phase 1) will permit (a) continued assessment of the maintenance of treatment effects on craving and cue reactivity to cocaine cues, and (b) assessment of generalization of DoR effects to novel cocaine picture cues (detailed below in the procedure section).

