Phase 1. In the proposed study, random effects ANOVA procedures will be used to assess differences among three treatment arms (placebo = PBO, 40 mg propranolol = 40PP, and 80 mg propranolol = 80PP). The over arching goal of the sample size estimation was to ensure the study will be sufficiently powered to adequately detect effect sizes that are both relevant to the study hypotheses and clinically meaningful. We restricted the Phase 1 estimation to the key outcome measure of subjective craving, as it has the largest standard deviation of all outcome measures. Drawing from the R21 results presented above, the subjective craving response following treatment with 40 mg of propranolol decreased 24.2 ± 24.7 points (mean \pm SD, change on a 100 point scale) while the group treated with placebo was found to decrease 8.8 ± 19.9 points. This yields a Cohen's d of $(15.4/22.3) = 0.69$. In the proposed study, we want to be able to detect craving differences, should they exist, between the PBO and 40PP group and between the 40PP and 80PP group. Additionally, we will make the conservative assumptions that (a) the difference between the PBO and 40PP groups will be 10% smaller than observed in the R21; $d = 13.9/22.3 = .62$, and (b) the difference between the 40PP and 80PP groups will be substantially (30%) smaller than the difference observed in the R21; $d = 11.6/22.3 = .52$. Accordingly, assuming

a pooled SD of 22.3, an $\alpha = .05$, and 60 participants randomized to each of three treatment groups, we will have 86% power to detect a $d = .62$ between the PBO and 40PP groups (i.e., craving difference of 13.9 units) and 80% power to detect a $d = .52$ between the 40PP and 80PP groups (i.e., craving difference of 11.6 units).

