Our research group has previously used this type of picture-based cue exposure procedure to successfully elicit craving in methamphetamine dependent individuals.^{69,70} Additionally, previous research by our group has shown that these pictures (subset of 10) elicit greater cocaine craving and subjective arousal in cocaine dependent individuals ($n = 27$; craving $\bar{x} = 5.9$ and arousal $\bar{x} = 10.1$) than in non-cocaine dependent controls ($n = 28$; craving $\bar{x} = .06$ and arousal $\bar{x} = 5.3$; both t 's > 3.6 , both p 's $< .001$). Furthermore, the mean craving and arousal reported by cocaine dependent individuals in response to the cocaine pictures was greater than the mean craving and arousal they reported in response to a set of neutral comparison pictures (craving $\bar{x} = 1.0$ and arousal $\bar{x} = 5.3$; both t 's > 4.5 , both p 's $< .0001$). Thus, we are confident these cocaine picture cues will serve as effective elicitors of craving and arousal in proposed study.

Procedure: At approximately 10:00 am, baseline subjective and physiologic outcome measures will be collected. Thirty minutes later, participants will receive the first sequence of CCE. Each sequence will consist of a 5-min video cocaine cue presentation followed immediately by in vivo cue presentation. Heart rate and SC data will be continuously collected during the first 50 sec of each cue type (video and in vivo). The CDMS Scale and BP will be obtained at the end of the in vivo cues. After the latter measures were obtained participants remained comfortably seated until the second, identical sequence of CCE commenced (approximately 5-10 min later). At the end of the CCE in the retrieval session, participants will receive their medication and complete all outcome measures. As indicated in figure 4, all dependent measures will be obtained immediately after CCE sequence and at 15 min. and 30 min. time points following termination of CCE. At the end of each retrieval session, research staff assisted the participant in removing the HR/SC leads and BP cuff. Participants will remain at the CTRC laboratory facility for an additional 60 min., at which time a blood draw will occur. The sample will

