The main cue reactivity outcome measures for the Phase 1 are subjective craving and physiological reactivity. Summary mean and peak values for craving (and related subjective measures) will be computed for all CCE sessions administered over the course of the study (i.e., all retrieval and test/follow-up sessions). Outcomes for the physiological measures (heart rate, skin conductance and blood pressure) will be computed in a similar fashion. However, data reduction on the HR and SC measures will precede computation of the summary values. The main cocaine use outcomes in Phase 2 will be (1) latency (days) to first use, (2) number of cocaine using days during follow-up, (3) dollar amount of cocaine used during follow-up, and (4) proportion of positive vs. negative UDS. Summary values on outcome measures obtained during the first retrieval CCE session (i.e., before any medication is administered) will serve as baseline (cue-elicited) outcomes and will be used as covariates in the data analytic plan described below.

Data Analysis Plan

Baseline demographic and clinical measures will be compared across treatment groups using standard statistical methods. Categorical demographic/clinical variables will be analyzed using Pearson chi square tests of independence while continuous demographic/clinical variables will be compared using one-way ANOVA procedures.

Phase 1. The first component of hypothesis 1 is that participants receiving propranolol (40 mg and 80 mg) compared to placebo treated controls, will evidence significantly lower cocaine craving and physiological reactivity (HR, SBP, DBP) during the first test/follow-up CCE session. To test this a priori hypothesis, a generalized linear mixed effects model will be developed using model-based estimates to construct group level contrasts (40PP & 80PP combined vs. PBO). A separate contrast will be developed to test the second component of hypothesis 1 that relative to the group 40PP, the group 80PP will evidence lower levels of craving and cue reactivity. Since the expected response pattern characterized in both components of hypothesis 1 is expected to occur to the novel picture cues presented at the end of the test session, a similar analytic plan will be adopted to evaluate the secondary hypothesis.

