Secondary Analysis. There are a number of secondary analyses of interest. First, it is possible that propranolol will begin affecting craving and cue reactivity as early as the second retrieval session. Therefore, we will use a linear mixed effects model to identify between group differences that develop in the second retrieval session. Second, it is expected that propranolol's ability to disrupt reconsolidation will be related to its bioavailability, which we will index using the plasma sample obtained approximately 90 min after each medication administration. We plan to use regression analyses to assess whether plasma concentrations of propranolol predict variation in the outcome measures (e.g., craving, cue reactivity and cocaine use) obtained across the test/follow-up CCE. Third, we plan to evaluate whether treatment impacts ambient or background craving and cue reactivity^{82,83} (i.e., non-cue-elicited outcomes obtained a half hour before each test/follow-up CCE session) using linear mixed effects models. The models will also test the effects of time and cocaine use status. Fourth, since there is some evidence of gender differences in propranolol metabolism^{84,85} and adrenergic functioning in emotional memory^{86,87}, we will examine associations between gender and treatment outcome. Fifth, we plan to evaluate the effectiveness of the participant blind. Specifically, responses obtained from the participants about which medication group (propranolol dose vs. placebo) they thought they were in will be contrasted with the medication condition to which they were randomized and analyzed via a Pearson chi square test of independence.

Missing Data. Since data for all medicated retrieval CCE sessions in Phase 1 will be collected while the participants are residing at the CTTC, missing data or study dropouts are not anticipated. Inevitably, over the 6-week follow up period, missing cue reactivity and cocaine use data will occur. The missing observations might be 'unit missing', which occurs when a participant does not present at one or more of the time points. The unit missing will be treated as though they are missing (completely) at random. Methods such as multiple imputations⁸⁸ using PROC MI and PROC MIANALYZE will be considered. With respect to the UDS data we will also perform a sensitivity analysis by treating any missing UDS as positive and reanalyzing the data.

I. Alternative Design Considerations and Potential Study Limitations

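### The background-craving analysis names no baseline covariate, and the matching pre-cue, pre-drug reading from the first retrieval session has no stated use in it

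*Combined protocol and SAP*

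**What the plan says.** Three places in the combined protocol and SAP bear on this point.

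- **Section 3.H, Secondary Analysis (third item).** The outcomes are "non-cue-elicited outcomes obtained a half hour before each test/follow-up CCE session". They are analysed by linear mixed models of the treatment effect, and "The models will also test the effects of time and cocaine use status". No baseline term is mentioned.
- **Section 3.H, Outcome Measures.** The plan's one rule on outcome baselines is that summary values from the first retrieval session, before any medication, "will serve as baseline (cue-elicited) outcomes and will be used as covariates in the data analytic plan described below". No exception or separate rule is given for the background outcomes.
- **Section 3.D, Procedure.** At about 10:00 am in the session, "baseline subjective and physiologic outcome measures will be collected. Thirty minutes later, participants will receive the first sequence of CCE". Medication follows the cues, so at the first retrieval session this reading is both pre-cue and pre-drug. Section 3.A confirms that measures "will be obtained at baseline and after stimulus presentations in all three CCE sessions" of Phase 1.

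Nothing in the documents assigns the first-session pre-cue reading to the background analysis, either as a covariate or as a baseline time point.

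**The concern.** The natural baseline for a repeated measure is the same measure, taken under the same conditions, before treatment. Here that value exists: same instruments, same half-hour lead before cues, no drug yet given. The plan as written leads to one of two models. If the Secondary Analysis text is taken alone, there is no baseline covariate. If the Outcome Measures rule is carried forward, the covariate is a cue-elicited summary, which mixes background level with response to cues. Neither model contains the outcome's own pre-drug value.

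Two things are at stake, both modest. The residual variance may be larger than it needs to be, and chance differences between arms in background craving at entry are not directly adjusted for. There is also some analyst freedom: the word baseline means a pre-cue reading in Section 3.D and a cue-elicited one in Section 3.H, so three different covariate choices could each be defended after the data are seen.

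**Working it through.** **Benchmark.** No power, SD, effect size or correlation is given for background craving, so there is no figure for this analysis to reproduce. The nearest is the Phase 2 figure in Section 3.B: 48 placebo against 96 combined propranolol, difference 5.6%, SD 11.3%, alpha .05, stated power 80%. With d = 5.6/11.3 = 0.496, a two-sided test gives 80.1% (normal approximation) or 79.5% (noncentral t). The stated figure reproduces.

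**Inputs for the illustration.**
- Group sizes: Section 3.B has "60 participants randomized to each of three treatment groups", so combined propranolol against placebo is 120 against 60. Applying that contrast to this outcome is an assumption.
- Two-sided alpha of .05.
- Effect: d = 0.445, chosen because it gives 79.9% power with no covariate. This is an assumption.
- Correlation r between the covariate and the outcome: assumed and varied.

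**Formula.** Adjusting for a covariate with correlation r multiplies the residual variance by (1 − r²), so the effective standardized difference is d/√(1 − r²). For r = .5 the variance falls by 25% and 0.445/√0.75 = 0.514.

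**Results (noncentral t, single visit).**

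| r of covariate with outcome | Power |
|---|---|
| none | 79.9% |
| .2 | 81.5% |
| .25 | 82.4% |
| .35 | 84.8% |
| .4 | 86.3% |
| .45 | 88.0% |
| .5 | 89.8% |
| .6 | 93.8% |

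**Pre-cue value in place of the cue-elicited value.**
- Pre-cue .5, cue-elicited .25 to .35: gain of 89.8 − 82.4 = 7.4 down to 89.8 − 84.8 = 5.0 points.
- Pre-cue .5, cue-elicited .45: gain of 89.8 − 88.0 = 1.8 points.
- Equal correlations: no gain.
- Pre-cue .4, cue-elicited .5: loss of 89.8 − 86.3 = 3.5 points.

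**Both covariates.** With correlations a (pre-cue) and b (cue-elicited) with the outcome and c with each other, R² = (a² + b² − 2abc)/(1 − c²). In the unfavourable case a = .4, b = .5, with c = .6 assumed, R² = (.16 + .25 − .24)/.64 = .266. This slightly exceeds the .25 from the cue-elicited value alone, and power is 90.4%. In every case run, power with both was no lower than with either one alone.

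**Repeated visits.** The planned analysis is a mixed model over the first test session and weeks 1, 3 and 6. For the average of four visits with between-visit correlation ρ, the adjusted variance is (1 + 3ρ)/4 − r² in units of the single-visit variance. At 96 against 48, with assumed ρ = .7 and d = .40 (normal approximation), power is 72.9% with no covariate, 78.1% at r = .3 and 87.8% at r = .5. The direction is the same; the size again depends on assumed values.

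**The case against.** The strongest reply is that the plan makes no wrong choice here. A reader might infer that the background analysis has been deliberately tied to a cue-elicited covariate. The documents do not support that: the Secondary Analysis text assigns no baseline covariate at all, and the link comes only from a general sentence that itself labels the covariates as cue-elicited. It is equally natural to read that sentence as serving the cue-elicited outcomes and to regard the background model's baseline as unspecified. This part of the reply stands, and the point is worded accordingly.

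A reader might also infer that a known amount of power is being lost. That is not supported either. It seems likely that the pre-cue value predicts later pre-cue values better than a cue-elicited summary does, but no correlation in the documents shows it, and the gain could be nil. The single-visit calculation also simplifies the planned mixed model.

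Nor is the treatment contrast biased. Assignment is randomized, with the urn balanced on gender and on dollar amount of cocaine use, the latter described as a likely prognostic factor for craving, and further factors may be controlled in analysis if needed. Chance imbalance in background craving is therefore a matter of precision. Those provisions do not name pre-cue craving, however, and so do not supply the missing covariate.

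Finally, this is the third of five secondary analyses, has no power claim, and does not bear on hypotheses 1 to 3. That limits the importance of the point but does not answer it.

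**Conclusion.** The point holds as a small, specific improvement. On either reading of the plan, the background outcomes are analysed without a stated use of their own pre-drug value, although it is scheduled to be collected. Using that value should improve precision to the extent that it predicts the later readings. From 80% unadjusted power, the illustration gives about 82% to 94% for correlations from .2 to .6. Relative to the cue-elicited covariate, the difference ranges from a small loss, through none at equal correlations, to a gain of about 5-7 points when the pre-cue correlation is .5 and the cue-elicited one .25 to .35. These figures rest on assumed correlations, an assumed effect size, the combined-propranolol contrast and a single visit; none is a documented loss. The severity is low: desirable, not required.

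**What to change.** In Section 3.H, under Outcome Measures or the third secondary analysis, add a sentence to this effect: the mixed models for background (non-cue) outcomes will adjust for the pre-cue reading of the same measure at the first retrieval session, alone or together with that session's cue-elicited summary. Choose between the two options before unblinding; including both guards against the case where the cue-elicited value turns out to be the better predictor. Keep the cue-elicited summary as the covariate for the cue-elicited outcomes.

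The cost is one sentence and one extra model term. No new data or visits are needed, because the reading is already scheduled before dosing, and the analyses of hypotheses 1 to 3 are unchanged.

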The primary goal of **Phase 2** will be to assess the effects of post-retrieval propranolol on indices of cocaine use obtained over a 6-week follow-up in which abstinence is no longer reinforced. Drug use will be retrospectively evaluated during weekly interviews using a calendar-based assessment and urine drug screens will be performed 3 times each week to provide an objective assessment of drug use/abstinence. At week 1, 3 and 6, laboratory-based test/follow-up CCE sessions (similar to identical to the test CCE session in Phase 1) will permit (a) continued assessment of the maintenance of treatment effects on craving and cue reactivity to cocaine cues, and (b) assessment of generalization of DoR effects to novel cocaine picture cues (detailed below in the procedure section).

B. Participants

A total of 180 non-treatment seeking, cocaine-dependent men and women (60 per treatment group), aged 18 or older, will be tested over a 54-month period (see Alternative Design Considerations section for a rationale pertaining to recruitment of non-treatment seekers). However, after getting close to the end of our recruitment we have found that 180 is not enough to collect the number of completers we need. We have increased enrollment to 200 in hopes to collect the number of completers we need to have significant power for statistical tests. This increase enrollment to approximately 67 per treatment group. Inclusion/exclusion criteria are detailed in the Protection of Human Subjects portion of this application.

Sample Size Estimation

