Phase 2. The phase 2 portion of the study was designed to assess group differences in cocaine use during the 6-week follow up. The previously completed R21 yielded an 86% follow up rate after a mean follow up time of 9 days. In the proposed study, we will conservatively estimate that there will be an 80% follow-up rate ($n = 144$ of randomized participants will be available for analysis), despite added reinforcement contingency for attending urine drug screen appointments and test/follow-up CE sessions. Although the R21 was not designed to assess the mean number of cocaine using days during follow-up and the number of days that each participant was followed was quite variable, we were able to estimate the standard deviation of the mean percent of using days to be approximately 11.3%. Therefore, assuming a similar common standard deviation in follow-up sample and with $\alpha = .05$, a sample of 48 participants in each treatment group, we will have 80% power to detect a difference in the mean percent of cocaine using days of 5.6% ($SD = 11.3\%$; Cohen's $d = .50$) between the propranolol treated (40PP & 80PP combined; $n = 96$) and placebo groups ($n = 48$). Additionally, assuming the same common standard deviation, α level, and group n , we would have 80% power to detect a mean percent cocaine using days difference of 6.5% between group 40PP and group 80PP. In either case, power will exceed 80% to detect differences that are both larger and more clinically substantive (e.g., 10%).

Recruitment

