The goals of the first test/follow-up session will be to evaluate the acute effects of dual medicated (either 40 and 80 mg propranolol) retrieval CCE sessions on craving and cue reactivity and to assess the generalization for these effects to novel cocaine cues picture cues. This session will be scheduled to occur no earlier than two days after inpatient discharge and no more than 4 days (this 2-4 days window will permit flexibility in scheduling to accommodate weekends and participant scheduling needs). The details of the first test/follow-up CCE session are identical to those described above for the retrieval sessions with the following exceptions. First, no medications will be administered. Second, UDS/breathalyzer assessment and Timeline Follow-Back will be administered to determine if the participant had maintained abstinence during the interim period (all participants, regardless of abstinence status, will be administered the CCE). Third, approximately 45 min after the CCE (i.e., 15 min after the 30 min post-CCE assessment; see shaded area in procedure Figure 4), the picture-based novel CCE procedure described above will be administered. At the end of the picture-based CCE, participants will complete 2 additional sets of post-cue measurements. Study staff will then remove the HR and SC leads and the participant will remain seated comfortably for 10 min. Prior to discharge, participants will be reminded that they are entering the follow-up phase (2) and that they are encouraged to remain abstinent from cocaine use but that abstinence will not affect the compensation that they receive for attending their scheduled follow-up sessions. In the event that a participant experiences elevated craving at the end of a CCE session (i.e., report a post-session craving score $\geq 20\%$ above baseline), they will be asked to remain in the CTTC until their craving subsides. A member of the research staff will be available to discuss management of craving urges. Finally, study staff and the participant will schedule the three study visits that will occur over the ensuing week.

E. Phase 2 Follow-up Drug Use Assessments and Cocaine Cue Exposure (CCE) Sessions

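### Phase 1 power allows for no loss before the outpatient test session, and its two stated power figures do not rest on the same number per group

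*Combined protocol and SAP*

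**What the plan says.** All references are to the combined protocol and SAP.

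- **Sample Size Estimation, Phase 1.** Power is given for "60 participants randomized to each of three treatment groups", with a pooled SD of 22.3 and alpha .05. It is stated as 86% for placebo vs 40 mg (d = .62, a "craving difference of 13.9 units") and 80% for 40 mg vs 80 mg (d = .52, a "craving difference of 11.6 units"). No loss is deducted.
- **Sample Size Estimation, Phase 2.** Here loss is deducted: "we will conservatively estimate that there will be an 80% follow-up rate", giving 144 analysed of 180, or 48 per group.
- **Section D (Phase 1 procedures).** On the first test/follow-up session: "This session will be scheduled to occur no earlier than two days after inpatient discharge and no more than 4 days". The Data Analysis Plan tests both components of hypothesis 1 at this session.
- **Section H, Missing Data.** The text says "missing data or study dropouts are not anticipated", and the reason given is that participants are inpatients during the medicated retrieval sessions. It then expects missing data over the 6-week follow-up, says that multiple imputation will be considered, and gives one sensitivity analysis, in which a missing urine drug screen counts as positive.
- **Section B, Participants.** "we have found that 180 is not enough to collect the number of completers we need", so enrolment rises to 200, about 67 per group. The Recruitment text adds that this allows for lost and withdrawn participants. The power paragraphs still rest on 180.

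**The concern.** The key Phase 1 outcome is craving at a visit made after discharge, when a participant can fail to return. The inpatient argument does not reach that visit, and the follow-up text starts after it. The planned handling of a missing test-session value is therefore unstated, and the power count treats every randomised participant as observed.

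At stake is mainly the 40 mg vs 80 mg contrast, the second component of hypothesis 1, whose stated power has almost no margin. In addition, two power figures from one sentence that imply different numbers per group cannot both be relied on. Neither paragraph was revised when enrolment went to 200.

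**Working it through.** **Inputs.** SD 22.3, alpha .05, differences 13.9 and 11.6, and 60 per group (Sample Size Estimation, Phase 1). Enrolment of 200 gives 200/3 = 66.7 per group (Participants). Sidedness is not stated; two-sided is assumed. No attendance rate for the test session is given, so a range is assumed. It includes 86%, the follow-up rate that the plan reports for the R21 at a mean of 9 days.

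**Formula.** Two-sample t-test with n per group: noncentrality = difference / (22.3 × √(2/n)), with 2n − 2 degrees of freedom. Power is the probability that the noncentral t exceeds the two-sided 5% critical value.

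**Step 1: reproduce the stated figures.**

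| Analysed per group | Placebo vs 40 mg (13.9) | 40 mg vs 80 mg (11.6) |
|---|---|---|
| 60 | 13.9/4.071 = 3.41; power 92% | 11.6/4.071 = 2.85; power 81% |
| 48 | 13.9/4.552 = 3.05; power 86% | 11.6/4.552 = 2.55; power 71% |
| Stated | 86% | 80% |

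The 80% fits 60 per group and the 86% fits 48. Testing each contrast at alpha .025 with 60 per group gives 87% and 72%, so that does not reconcile them either. No single setting tried gives both figures.

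**Step 2: margin on the dose contrast.** Power is 80.0% at 59 per group and 79.3% at 58. The plan can lose one participant per group before falling below 80%.

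**Step 3: assumed attendance at the test session, 40 mg vs 80 mg.**

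| Attendance | From 60 per group | Power | From 66.7 per group | Power |
|---|---|---|---|---|
| 95% | 57 | 79% | 63.3 | 83% |
| 90% | 54 | 76% | 60 | 81% |
| 86% | 51.6 | 74% | 57.3 | 79% |
| 80% | 48 | 71% | 53.3 | 76% |

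With 200 enrolled, 80% power holds down to 59/66.7 = 88.5% attendance. For placebo vs 40 mg, 80% of 60 leaves 48 per group and about 85% power (85.6% from 13.9/22.3; 85.2% from the rounded d = .62).

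**Step 4: what the increase to 200 implies.** If the target is 144 Phase 2 completers, 144/200 = 72% retention. If the target is 180 at the Phase 1 test session, 180/200 = 90%. The documents state neither target. The Phase 2 figures themselves reproduce: 5.6/11.3 with 96 vs 48 gives 79.5%, and 6.5/11.3 with 48 vs 48 gives 79.6%.

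**Separate slip in the same paragraph, not used above.** A difference 30% below 15.4 is 15.4 × 0.7 = 10.8, not 11.6. It should be settled when the paragraph is restated.

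**The case against.** Five arguments weigh against the point.

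1. **Retention to the test session is well supported.** Section G holds Phase 1 payment until that visit and pays extra for attending on schedule. Section D runs the cue exposure whatever the abstinence status, so relapse alone does not remove the outcome. The R21's 86% was at about 9 days, not 2-4. This stands: loss may be small. Incentives do not make attendance complete, however, and the $75 tied to a negative screen gives less reason to return to someone who has used cocaine.
2. **The increase to 200 repairs most of the shortfall.** This stands if loss is about 10% or less.
3. **The dose contrast is the most fragile one.** The first component of hypothesis 1 pools both propranolol groups. If d = .62 is assumed for that contrast, 96 vs 48 still gives 94%. This stands, and the point is limited accordingly.
4. **Baseline adjustment will help.** The SD is for change scores, while the plan uses first-retrieval values as covariates. With equal session variances, adjustment multiplies the change-score variance by (1 + r)/2. The documents give no r. For assumed r of .5, .6, .7 and .8, dose-contrast power at 48 per group is 83.0%, 80.5%, 78.1% and 75.8%, against 71% unadjusted. This stands as a caveat, but the plan's own figures take no credit for adjustment.
5. **The 86% fits 48 per group, so it may already include 20% loss.** Possibly, but the sentence says 60, and the 80% beside it holds only at 60.

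A reader might also infer that the plan asserts zero loss at the test session. It does not: the sentence is tied to the retrieval sessions, and the text is silent on the test session.

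**Conclusion.** The point holds in limited form. Phase 1 power as written allows for no loss before the visit at which hypothesis 1 is measured, that visit has no missing-data rule, and the two stated powers do not come from one n. For 40 mg vs 80 mg, unadjusted power falls from 81% to between 79% and 71% over assumed attendance of 95% to 80% of 60 per group. With 200 enrolled it is 81%, 79% and 76% at 90%, 86% and 80%. The placebo contrasts are not endangered within this range. These sizes assume a two-sided test, equal groups, all 200 randomised, and the stated SD and differences.

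A reader might infer that raising enrolment to 200 contradicts the 80% Phase 2 retention. The documents do not support that. They do not define completer, give the target, report observed retention, or say in which phase participants were lost. The increase shows that a completion assumption failed, but not which one. The 72% figure follows only if 144 Phase 2 completers is the target.

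**What to change.** 1. Define completer, and state the target number and the phase to which it applies.
2. Restate both power paragraphs for 200 enrolled. Use the number expected at the test session for Phase 1 and at follow-up for Phase 2. Use one n, one alpha and a stated sidedness for both Phase 1 contrasts. If credit is taken for baseline adjustment, state the assumed correlation.
3. Limit the sentence on no anticipated loss to the inpatient retrieval sessions, and add the test session to the missing-data plan.
4. Fit hypothesis 1 as a mixed model that includes the retrieval-session values of all randomised participants, under missing at random. This mainly guards against bias; a participant without a test-session value adds little precision.
5. Add a sensitivity analysis suited to a continuous outcome, for example imputation with a range of shifts for missing values. The missing-as-positive rule for urine screens has no counterpart for craving or heart rate.

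The cost is wording in the sample-size and analysis sections, with no patients beyond the 200 already planned. The stated power for the dose contrast becomes somewhat less favourable if loss exceeds about 10%.
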